#### **12.3. Final Analytic Plan**

Categorical data will be described using descriptive statistics (proportions and percentages). Continuous data will be described using means and standard deviations (normally distributed data) or using medians and interquartile range (non-parametric data). Appropriate comparative statistical tests will be chosen based

in the variable types (categorical, dichotomous, continuous) and distribution (parametric, non-parametric) and will be used to describe significant differences between intervention and control groups. Where appropriate, point estimates and confidence intervals will be reported. The p-value will be two tailed with a significance level of 0.05.

The microbiome will be assessed using 16s rRNA targeted amplicon sequencing. Sequences will be cleaned and binned into operational taxonomic units and assigned taxonomy. Differences within individuals will be assessed using the Inverse Simpsons Diversity index and comparisons between study groups will be done using the Bray Curtis dissimilarity matrix and visualized using principal coordinates analysis.

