## 2. STUDY SUMMARY

Title	A phase II randomized, double-blind placebo-controlled trial to determine if fecal microbiota transplantation is efficacious for hospitalized patients with C. difficile infection history during antibiotic treatment
Short Title and Precis	The GRAFT study
Protocol Number	2017-0789
ClinicalTrials.gov number	NCT03621657
Funding Sponsor	Agency for Healthcare Research and Quality (AHRQ) [name] [contact]
Study Product	OpenBiome fecal microbiota preparation capsule [FMT Capsule DE]
Phase	Phase II study
Methodology	Randomized, double-blind, placebo-controlled trial
Study Duration	1 year
Study Center(s)	Single-center, University of Wisconsin Hospitals and Clinics
Objectives	The primary objective of this study is to compare the gut microbiota and clinical outcomes of oral FMT during antibiotic treatment, immediately following antibiotic treatment, and placebo. The second objective is to assess the safety and feasibility of daily oral Fecal Microbiome Transplant (FMT) as a treatment option.
Number of Subjects	30 (1:1:1 randomization), 10 subjects per group
Diagnosis	Changes in the gut microbiota and C. difficile infection (CDI)
Main Inclusion Criteria	Receiving antibiotics for reasons other than CDI following a recent CDI episode (within last 90 days)
Main Exclusion Criteria	Bowel obstruction or gut motility issues, severely immunocompromised, or admitted to the ICU.
Study Product, Dose, Route, Regimen	FMT will be delivered through oral capsules prepared by OpenBiome. It will be administered in one of two ways depending on the arm of the trial. 1) A low dose of 5 capsules per day during antibiotic treatment and for seven days following conclusion of antibiotics. 2) A single dose of 30 capsules (22.5g) of oral FMT will be given 48-72 hours after antibiotic treatment conclusion.
FDA status of product	Encapsulated fecal microbiota preparation (FMT Capsule DE). Please refer to Finch Therapeutics BBMF # 17194.
	Sourced from human-derived microbes. Please refer to OpenBiome BBMF # 15543, Section F.
	IND: 18262

**Duration of administration** Group 1: 5 capsules of oral FMT per day undergoing antibiotic treatment and for 7 days following conclusion of antibiotic treatment.

Group 2: 30 capsules taken 48-72 hours following conclusion of antibiotic treatment

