### **6. STUDY OBJECTIVES AND PURPOSE**

The goal of this study is to assess the effect of daily oral FMT and a single dose FMT on the gut microbiota in patients currently undergoing antibiotic treatment.

- Primary Objective: To assess the efficacy of oral FMT on the composition and function of the gut microbiota compared to the placebo groups.
- Secondary Objective: To assess the safety and feasibility of both oral FMT regimens versus placebo.
- Secondary Objective: To determine the rate of CDI during oral FMT versus placebo.
- Secondary Objective: To determine the rate of *C. difficile* colonization during oral FMT compared to placebo.
- Secondary Objective: To evaluate time to CDI and/or colonization with *C. difficile*.

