### **7. STUDY DESIGN AND ENDPOINTS**

#### **7.1. General Design**

This is a phase II, double-blind, randomized, placebo controlled trial assessing the effects of either daily (group 1) or one-time (group 2) oral FMT on the composition and function of the gut microbiome compared to placebo (group 3) in a population of patients with a history of CDI currently on antibiotics for a reason other than current CDI. Participants will be 18 years of age or older, have 72 hours or less of an antibiotic and meet all inclusion criteria while having no exclusion criteria prior to randomization. Patients will be randomized at a 1:1:1 ratio using permuted blocks (block size=10). Randomization will be double-blinded. Each subject (n=30) will be followed for 6 months. Stool samples will be taken at baseline and every 3 days  $\pm$  1 day from all subjects regardless of treatment group while the patient is hospitalized. If/when a patient is discharged from the hospital, the patient will continue to provide stool samples every three days during FMT. Following completion of the FMT intervention, the patient will provide stool samples once weekly for the 1 month follow-up period. All patients will be asked to complete a patient diary to report diarrhea history.

Up to one gram of stool will be sent to Finch therapeutics for additional 16s rRNA sequencing.

**Intervention:** There are 2 intervention groups for this study. Both groups will receive oral FMT capsules from OpenBiome for the prevention of CDI during antibiotic treatment. All patients will fast (clear liquids only) for a minimum of 2 hours prior to administration and 1-hour post-administration for the daily groups and be fasting for 8 hours prior and 1 hour post FMT consumption for the single dose group. The capsules will be administered in the patient's room while admitted or in the ID clinic or CRU if the patient is an outpatient and the first dose will occur under direct observation. Patients admitted to the hospital as well as all patients in the single dose group will be observed for 30 minutes post-administration to ensure the capsules are safely consumed. Hospitalized patients need to be observed 30-minutes post-administration following only the first dose. As mentioned above, the oral FMT capsules will be administered in two ways:

**Group 1:** This group will receive daily oral FMT capsules. Five capsules will be administered each day of the

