patient's antibiotic treatment plus seven days post-antibiotic treatment.

**Group 2:** This group will receive 30 oral FMT capsules one time 48-72 hours following completion of antibiotic treatment.

**Oral FMT capsules:** Capsules contain fecal microbiota sourced from healthy donors and screened for pathogens.

**Control:** The control is an oral placebo capsule identical to the FMT capsules given to the intervention groups and will be provided by OpenBiome. The placebo capsule consists of glycerol and saline and will be administered daily as five capsules per day during the duration of antibiotic treatment plus an additional seven days post-antibiotic treatment (group 3). Patients will be fasting (clear liquids allowed) for at least 2 hours prior to administration and at a minimum of 1-hr post-administration (Appendix 17.1)

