### *All subjects:*

All subjects will provide stool samples every three days after the baseline visit until their FMT intervention is complete and weekly for one month following conclusion of FMT treatment. Patients will also be asked to complete a patient diary daily from enrollment through the first month of follow-up. If a subject is discharged during the study period, he/she will be asked to complete the patient diary from home as well as provide stool samples to be mailed back to the lab for processing. A member of the study team will also call or email patients on a weekly basis during the intervention and follow-up period to remind to complete the stool sample

as well as record any adverse events. If a patient is discharged, vital signs, general health status, and medications at discharge will be assessed through the medical record.

At the end of the 1 month follow-up (last week of providing the weekly, post-FMT stool samples), patients will receive a call assessing the following:

- Clinical assessment by study nurse or physician, specifically evaluating adverse events related to the intervention.
- Data collection at visit:
  - Interim medical history with focus on infectious diseases
  - Concomitant medication
  - Significant changes in diet
  - Changes in stool consistency (Bristol Stool Scale) and frequency
  - General health status
  - Adverse events (NIH criteria)

A table of all study events is provided in Appendix II, 17.2 (Study Calendar).

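### Section 12.3 should say that the single-dose group's stools before its dose are not FMT-exposed, and could use them as supplementary controls for daily FMT during antibiotics

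*Combined protocol and SAP*

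**What the plan says.** The Study Summary (Section 2) gives the primary objective as to "compare the gut microbiota and clinical outcomes of oral FMT during antibiotic treatment, immediately following antibiotic treatment, and placebo". Section 6 words it as "To assess the efficacy of oral FMT on the composition and function of the gut microbiota compared to the placebo groups". Section 7.2.1 places the primary outcome, gut composition and function, in the setting of concurrent antibiotics, with stools continuing for a month after the intervention.

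Section 7.1 names two intervention groups, daily FMT (Group 1) and single-dose FMT (Group 2), and defines the control as daily placebo (Group 3). Of Group 2 it says: "This group will receive 30 oral FMT capsules one time 48-72 hours following completion of antibiotic treatment". Section 11.2 applies one stool schedule to everyone: "All subjects will provide stool samples every three days after the baseline visit until their FMT intervention is complete".

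Section 12.3 says suitable tests "will be used to describe significant differences between intervention and control groups", and that "The p-value will be two tailed with a significance level of 0.05". It separately plans Bray-Curtis comparisons between study groups. The Statistical Methodology entry in Section 2 adds ANCOVA and linear mixed models for the longitudinal data. The size is "30 (1:1:1 randomization), 10 subjects per group", with a goal of 8 analyzable per group (Sections 8.1 and 12.2). Section 12.1 calls the trial a pilot not sized by a hypothesis test.

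No section says how Group 2's stools before its dose are to be classified, or defines an on-antibiotic window.

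**The concern.** During antibiotics the randomized groups do not divide into FMT and control as Sections 7.1 and 12.3 label them. Group 2 is an intervention group by name, but for courses within 14 days it is untreated throughout that period.

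Two things follow. If an analyst takes the two-way split in Section 12.3 at its word and pools Groups 1 and 2, untreated stools dilute the estimated effect of daily FMT on antibiotics. And concurrently randomized, FMT-free patients whose stools are already being collected add nothing as controls in a trial too small to spare them.

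**Working it through.** **Inputs.** From the documents: two-sided 0.05 (12.3); 10 per group, 8 analyzable (2, 12.2). The plan gives no effect size or SD, so effects are assumed, in between-patient SDs, for one continuous summary per patient. The plan has no power figure to reproduce.

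**Step 1: who is FMT-free on antibiotics.** With courses within 14 days, 10 placebo + 10 single-dose = 20 patients. The defined control is 10 of these (8 of 16 at the analyzable target).

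**Step 2: dilution if Groups 1 and 2 are pooled.** If daily FMT shifts Group 1 by d and Group 2 is untreated, the pooled mean shift is (10 × d + 10 × 0)/20 = d/2. A true 1.0 SD effect appears as 0.5 SD. With 20 vs 10, power to detect 0.5 SD is 24%, against 56% for Group 1 vs Group 3 at 1.0 SD. This ignores the extra spread from mixing the groups.

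**Step 3: precision of the daily-FMT contrast.** SE = SD × √(1/n₁ + 1/n₂); half-width = t(0.975, n₁+n₂−2) × SE.

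| Group 1 vs controls | SE (SD) | t | 95% half-width (SD) |
|---|---|---|---|
| 10 vs 10 | √0.200 = 0.447 | 2.101 | 0.94 |
| 10 vs 20 | √0.150 = 0.387 | 2.048 | 0.79 |
| 8 vs 8 | √0.250 = 0.500 | 2.145 | 1.07 |
| 8 vs 16 | √0.1875 = 0.433 | 2.074 | 0.90 |

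The SE ratio is √(0.150/0.200) = 0.866, so 13% smaller. Variance falls 25%, equivalent to 2/0.150 = 13.3 per arm at 1:1.

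**Step 4: power.** Noncentral t, df = n₁+n₂−2, noncentrality d/√(1/n₁+1/n₂).

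| Assumed effect | 10 vs 10 | 10 vs 20 | 8 vs 8 | 8 vs 16 |
|---|---|---|---|---|
| 0.5 SD | 18% | 24% | 15% | 20% |
| 1.0 SD | 56% | 70% | 46% | 60% |
| 1.2 SD | 72% | 85% | 61% | 75% |

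The effect detectable with 80% power falls from about 1.32 to 1.12 SD (10 per arm), or from 1.51 to 1.27 SD (8 per arm).

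**Step 5: how much data the window holds.** Section 8.4.1 focuses initial recruitment on infections with short courses, and Section 8.2 allows up to 72 hours of antibiotics before enrollment. Assuming courses of 5 to 14 days with 0 to 3 days elapsed, 2 to 14 on-antibiotic days remain. At one stool every 3 days that is roughly 0 to 4 post-baseline stools, so some patients may contribute none. Steps 3 and 4 assume that everyone contributes.

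**Step 6: courses over 14 days.** Section 8.4.2.2 gives a 30-capsule dose on day 16 or 17 of antibiotics, so a patient dosed that way is not FMT-free until antibiotics end. That section assigns the 30-capsule dose to Group 1 and the stopping of daily dosing to Groups 2 and 3. This contradicts the group definitions in Section 7.1, and the two must be reconciled.

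**The case against.** A reader might infer that the plan has chosen to compare daily FMT with placebo alone and wastes half its controls on its main question. The documents do not support that.

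- **The contrast is unspecified, not wrongly chosen.** Section 12.3 names no exact contrast and also plans comparisons between study groups. A three-arm mixed model of the kind listed in Section 2 would already use Group 2's stools for the error variance. With a three-arm pooled variance (27 df), 10 vs 10 gives 58% power at 1.0 SD and a half-width of 0.92 SD, so the extra gain is slightly smaller than tabulated. Such a model still would not use Group 2 as a control.
- **Half is a headcount.** The standard error falls 13%.
- **The question is narrower than the protocol's.** The primary outcome runs on through the intervention and a further month, and Group 1 is dosed for 7 days after antibiotics. Pooling must stop at Group 2's dose, so it helps with little of the 7-day tail and none of the month.

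The objection to exchangeability also stands. Group 2 takes no capsules on antibiotics, has no daily fasting and is not masked to regimen. Its test capsule and pregnancy test come at the post-antibiotic dosing visit (Section 17.2), so a completers-only analysis would select Group 2 differently. Comparing Group 2 with Group 3 cannot settle whether placebo is inert: at 10 vs 10 its half-width is 0.94 SD. These are reasons to keep the masked placebo comparison as the main one. They do not justify leaving Group 2's untreated stools labelled as intervention.

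**Conclusion.** The concern holds as a gap in specification with a cheap, moderate remedy. Section 12.3 leaves open a reading that counts untreated stools as FMT-exposed, which would halve the apparent daily-FMT effect in that window if Groups 1 and 2 were pooled. It also makes no use of Group 2 as a control before its dose.

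The gain from a pooled contrast is worthwhile only if effects are large. It rests on assumed effect sizes, a continuous per-patient summary, a usable stool from each patient in the window, and no effect of saline/glycerol capsules or fasting on the microbiota. The figures do not carry over to binary PCR colonization or to Bray-Curtis distances. Exactly 10 per group is itself not assured, because blocks of 10 cannot be divided 1:1:1. The pooled contrast should be supplementary and should not replace the placebo comparison.

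**What to change.** Add a paragraph to Section 12.3, before data are seen, stating that:

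1. Group 2's stools before its dose are not analysed as FMT-exposed.
2. Group 1 vs Group 3 is the masked main comparison.
3. A supplementary contrast compares Group 1 with Groups 2 and 3 combined, on diversity and *C. difficile* PCR colonization. Patients are analysed by randomized group and not as completers, with adjustment for the baseline value where this is defined.
4. The window runs from randomization to the earliest of the last antibiotic day, day 14 of antibiotics, or Group 2's dose.
5. Group 2 vs Group 3 over the same window is reported descriptively, with the caution that it is too imprecise to show that placebo has no effect.
6. After Group 2's dose, the three arms are kept separate.

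Separately, reconcile the group labels for courses over 14 days in Section 8.4.2.2 with Section 7.1, since the window depends on them.

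The cost is one paragraph and one extra model on samples already planned, with no new patient, visit or assay. The price is the untestable assumption about placebo capsules and fasting, which is why the masked comparison stays in front.

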#### **12.4. Source Documents and Access to Source Data/Documents**

We will maintain appropriate medical and research records for this trial, in compliance with ICH E6 GCP, Section 4.9, and regulatory and institutional requirements for the protection of confidentiality of participants. Forms for use as source documents will be derived from the electronic CRFs. Additional source data include records of clinical findings, observations, or other activities in a clinical trial necessary for the reconstruction and evaluation of the trial. Examples of these documents and data records include, but are not limited to, hospital records, clinical and office charts, laboratory notes, memoranda, pharmacy dispensing records, recorded data from automated instruments, copies or transcriptions certified after verification as being accurate and complete, microfiches, photographic negatives, microfilm or magnetic media, imaging, and participant files and records kept at the pharmacy, laboratories, and medico-technical departments involved in the clinical trial.

The study protocol, documentation, data, and all other information generated will be held in strict confidence. No information concerning the study or the data will be released to any unauthorized third party without prior written approval from the PI.

The study monitor or other authorized representatives of the research team and FDA may inspect all documents and records required to be maintained by the Investigator, including, but not limited to, medical records (office, clinic, or hospital) and pharmacy records for the participants in this study. The clinical study site will permit access to such records.

All samples and forms will be encoded (labeled) only with a barcode and a unique tracking number to protect participant's confidentiality.

Up to one gram of stool from each collected sample will be sent to Finch therapeutics for additional 16s rRNA sequencing. Samples sent to Finch will be de-identified.

#### **12.5. Quality Management System**

The monitoring of subjects enrolled in this study includes both internal and external activities governing the administration of the investigational product. Internal monitoring is performed by members of the study team and external monitoring by a team of staff not involved in the conduct of study procedures with the appropriate clinical and technical expertise.

##### **12.5.1. Study Team Training**

The PI will ensure that members of the study team are appropriately qualified and trained on the protocol, and/or on study procedures applicable to their delegated roles/responsibilities. When the protocol and/or methods to conduct study procedures are updated, staff are retrained prior to performing any study-related activities described in the updated document. All training is documented and maintained in the study files.

Per University of Wisconsin-Madison policy, all personnel engaging in human subjects research must also complete Human Subjects Protection, Good Clinical Practice (GCP), and Health Insurance Portability and Accountability Act (HIPAA) training.

#### **12.5.2. Standardized Procedures**

A Manual of Procedures (MOP) has been created for this study to supplement the study protocol by providing additional details on the conduct of the study and study procedures. It is routinely updated to ensure consistent performance of study activities.

#### **12.5.3. Internal Quality Monitoring**

Members of the study team will conduct internal monitoring activities in real time when completing the study records and following each study visit. These activities will include, but are not limited to, periodic review of completed data collection forms, eligibility records, regulatory files and electronic data. Reviews will be performed by a different individual than those involved in data entry.

#### **12.5.4. External Quality Monitoring**

The purpose of external study monitoring is to ensure compliance with applicable regulations (21 CFR 312 and GCP), which require monitors to verify that:

- The rights and well-being of human subjects are protected.
- Reported study data are accurate, complete, and verifiable from source documentation.
- The conduct of the trial is in compliance with the currently approved protocol and all applicable regulatory requirements.

The sponsor-investigator has contracted with UW ICTR Study Monitoring Service. Refer to the ICTR SMS Monitoring Plan and Service Agreement for more information. The PI will provide direct access to all trial-related sites, source data/documents, and reports for the purpose of monitoring and auditing, and inspection by local and regulatory authorities.

#### **12.5.5. Database Quality Control (QC)**

QC procedures regarding data entry will be implemented. Regular data quality control checks will be run on the database. Any missing data or data anomalies will be assessed for clarification and resolution.

### **12.6. Data Capture**

#### **12.6.1. Case Report Forms**

The study case report form (CRF) is a data reporting instrument for the study. All data requested on the CRF must be recorded. All missing data must be explained. All entries should be printed legibly in black ink. If any entry error has been made, to correct such an error, a single straight line is drawn through the incorrect entry and the correct data is entered above/near the correction. All such changes must be initialed and dated.

#### **12.6.2. Data Collection Tools**

Clinical data (including AEs, concomitant medications, and solicited events data) and clinical laboratory data will be entered into a secure, web-based Research Electronic Data Capture (REDCap) system. The data system includes password protection and internal quality checks, such as automatic range checks, to identify data that appear inconsistent, incomplete, or inaccurate. Clinical data will be entered directly from the source documents.

### **12.7. Records Retention**

Study files (except for future use consent forms) must be maintained for a minimum of two years after the

last approval of a marketing application in an ICH region and until there are no pending or contemplated marketing applications in an ICH region or at least 2 years have elapsed since the formal discontinuation of clinical development of the investigational product. These documents should be retained for a longer period, however, if required by local regulations. No records will be destroyed without the written consent of the lead PI or designate, if applicable. It is the responsibility of the lead PI or designate to inform the site PIs when these documents no longer need to be retained. Consent forms for future use will be maintained as long as the sample exists.

